6.1 Investigational and control drugs

Investigational drug

- **Certican®**

Active ingredient: Everolimus (RAD001)
Galenic form: tablets
Dose: one tablet containing 0.25 mg, 0.75 mg or 1.0 mg
Dosing schedule: based on drug level (5 – 10 ng/mL).
Packaging: blisters of 10 tablets

Other components of the immunosuppressive regimen

- **Prograf®**

Active ingredient: Tacrolimus
Galenic form: capsules

Dose: one capsule containing 0.5 mg, 1.0 mg and 5.0 mg
Dosing schedule: according to blood level
Packaging: trade ware will be used

• **Sandimmun® Optoral**

Active ingredient: Cyclosporin A
Galenic form: capsules
Dose: one capsule containing 10 mg, 25 mg, 50 mg, or 100 mg
Dosing schedule: according to blood levels (cf. [Table 4-1](#) and [section 6.5.2](#))
Packaging: trade ware will be used

• **Mycophenolic Acid (MPA)**

based on investigator's decision, one of the following drugs will be used:

Myfortic®

Active ingredient: Enteric Coated Mycophenolate Sodium (EC-MPS)
Galenic form: tablets
Dose: one tablet containing 180 mg or 360 mg
Dosing schedule: 1440 – 2880 mg/day, if tolerated
Packaging: trade ware will be used

CellCept®

Active ingredient: Mycophenolate Mofetil (MMF)
Galenic form: capsules / tablets
Dose: one capsule containing 250 mg or
one tablet containing 500 mg
Dosing schedule: 1500 – 3000 mg/day, if tolerated
Packaging: trade ware will be used

• **Corticosteroids**

according to local standard. A dose of 0.05 – 0.3 mg/kg prednisolone or equivalent should be continued throughout the trial.

6.2 Treatment groups

The day after Screening visit, during the run in phase, all patients will receive the following immunosuppressive therapy:

Cyclosporin A (C0level: 100-200 ng/mL) or Tacrolimus (C0level: 5 - 10 ng/mL) and Everolimus (C0level: 5-10 ng/mL) or MPA and corticosteroids.

At Baseline visit (Month 6 post Tx) patients will be assigned to one of the following two treatment groups in a ratio of 1:1:

- **Maintenance** of immunosuppressive **CNI-based regimen** (CNI group):
Cyclosporin A (C0: 50 – 150 ng/mL) or Tacrolimus (C0: 3 – 8 ng/mL)+
Everolimus (C0: 5 – 10 ng/mL) +
Corticosteroids
- **Switch to CNI-free regimen** (CNI-free group):
MPA (MMF 1500 - 3000 mg/day OR EC-MPS 1440 - 2880 mg/day) +
Everolimus (C0: 5 – 10 ng/mL) +
Corticosteroids +
Cyclosporin A ≤ 75 ng/mL (according to -evel) (months 6-9) or Tacrolimus ≤ 5 ng/mL (according to C0) (months 6-9)

6.3 Treatment assignment

A randomization list will be produced by or under the responsibility of Novartis Biometrics Department using a validated system that automates the random assignment of treatment groups to randomization numbers in the specified 1:1 ratio (CNI group, CNI-free group). The randomization scheme will be reviewed and locked after approval. According to the recommendations given in the ICH E9 Guideline “Statistical Principles for Clinical Trials” (CPMP, 1998), the used block length is specified in a separate document which is withhold from the study centers. The randomization list will be kept sealed in a secure location.

At Enrollment (Screening Visit – Month 3 post Tx), patients will be assigned a unique patient identification number by the investigator. The patient identification number has two parts. The first part is the four-digit center number, which is assigned by Novartis. The second part will be assigned by the investigator starting with number “00001” in each study site. Once assigned to a patient, the patient identification number will not be reused. If the patient fails to be enrolled into the study for any reason, the patient’s identification number and the reason for not being enrolled will be entered on the Screening Failure Log. Note: The patient identification number is different from the randomization number.

At Baseline visit (Month 6 post Tx), all eligible patients will be given a randomization number that assigns them to one of the treatment groups. The randomization numbers are sequentially allocated to the patients per center in the order of inclusion in the randomized treatment period.

Randomization of individual patients will be performed centrally by a CRO [REDACTED]
[REDACTED]. Allocation of a patient to one of the two treatment groups will be performed in the following steps.

1. Information about patient enrollment (Screening Visit – Month 3 post Tx):
Study sites will inform the randomization department of the [REDACTED]
[REDACTED] about each patient inclusion via fax.

2. Randomization (Baseline Visit – Month 6 post Tx):
At day of randomization, the site will provide the information of eligible patient to [REDACTED] by fax.
[REDACTED] randomization department will allocate the patient the next free consecutive randomization number allocated to the site. Randomization number and allocated treatment (according to the randomization list) will be provided to the site by fax.

The randomization number will be entered on the CRF of an individual patient.

6.4 Treatment blinding

This is an open-label study.

6.5 Treating the patient

6.5.1 Study drug administration

Everolimus is study drug from month 3 (visit 1). Before month 3 the patient will receive a prescription for Everolimus, the use of Everolimus before visit 1 is not excluded. Each study site will be supplied by Novartis with study drug (Everolimus). Study drug will be provided as tablets, packaged in boxes containing strips of blister packed tablets, and labeled as RAD001 Tablets. Study drug will be available in 0.25, 0.75, and 1.0 mg strength. One component of the box consists of a 2-part label which includes an identifier of each single box of study medication. Before dispensing the study medication to an individual patient, investigator staff must enter the 4-digit patient number and the date of dispensing of the medication box on both parts of the label. The outer part of the label will be detached from the packaging and affixed to the source document (Drug Label Form in the CRF) containing that patient's unique patient number.

For the other immunosuppressive drugs (Cyclosporin A, Tacrolimus, MPA, corticosteroids) the patient will receive a prescription.

The prescribed total daily dosage of the immunosuppressive drugs should be divided in two (equal) doses, applied 12 hours apart (i.e. 08:00 a.m. and 08:00 p.m.).

The investigator should instruct the patient to take the study drug exactly as prescribed in order to promote compliance. All dosages prescribed and dispensed to the patient and all dose changes during the study must be recorded on the Dosage Administration Record CRF.

In patients randomized to the CNI-free group, withdrawal of Cyclosporin A or Tacrolimus and commencement of MPA or Everolimus will be performed starting the day after randomization at Month 6 post Tx.

In a first step the Cyclosporin A should be decreased to a dose resulting in a C0 blood level of \leq 75 ng/mL for 8 weeks, and Tacrolimus should be decreased to a dose resulting in a level of \leq 5 ng/mL. MPA or Everolimus should be introduced. Further increase / adjustment of MPA or Everolimus and removal of Cyclosporin A or Tacrolimus should be performed based on the investigator's experience and the given clinical conditions, adverse events, etc. The CNI-free regimen should be achieved after a CNI reduction / elimination period of maximum of 3 months (starting from Month 6 post Tx and be stable by Month 9 post Tx).

In cases of recurrent infections serum antibody concentration should be measured; if hypogammaglobulinemia presents as persistent and clinically significant, patients should be examined accurately and appropriate actions should be taken; dose reduction or change of immunosuppression should be taken into consideration.

Patients with recurrent pulmonary disorders e.g. cough/dyspnea should as soon as possible be examined accurately for signs of bronchiectasis; dose reduction or change of immunosuppression should be taken into consideration.

Corticosteroids must be added to the immunosuppressive regimen in all patients, according to local standard. A dose of 0.05 – 0.3 mg/kg prednisolone or equivalent should be continued throughout the whole study.

Safety recommendations regarding the use of MPA:

MPA is a powerful human teratogen, which increases the risk of spontaneous abortions and congenital malformations in case of exposure during pregnancy. Therefore following safety recommendations should be followed for all patients that are receiving MPA (f.ex. CellCept or myfortic).

Investigators should ensure that women and men that are receiving MPA understand the risk of harm to the baby, the need for effective contraception, and the need to immediately consult responsible investigator if there is a possibility of pregnancy or a suspected gap of contraception. In addition, patients should not donate blood during therapy or for at least 6 weeks following discontinuation of MPA.

Recommendations for female patients:

Before starting treatment with MPA, women of child bearing potential must have undergone pregnancy testing, i.e. done at Screening, Baseline, Switch and following study visits (Assessment Schedule Table 7-1) in order to exclude unintended exposure of the embryo to mycophenolate. A pregnancy β -HCG test is mandatory for all female patients in this trial at all indicated visits (Table 7-1).

Pregnancy tests should be repeated as clinically required (e.g. after any gap in contraception is reported). Results of all pregnancy tests should be discussed with the patient.

Women of childbearing potential should use two reliable forms of contraception simultaneously before starting therapy, during therapy, and for six weeks after stopping treatment with MPA.

Recommendations for male patients

Sexually active men (including vasectomized men) are recommended to use condoms during treatment and for at least 90 days after cessation of treatment. In addition, female partners of male patients treated with MPA are recommended to use highly effective contraception during treatment and for a total of 90 days after the last dose.

Men should not donate semen during therapy with MPA or for 90 days following discontinuation of MPA.

Table 6-1 Schematic diagram of medication administration

Phase	No Study	Prephase	Study Drug Treatment						
			Run In	BL	Switch	Maintenance			
Visit		1	2	3	4	5	6	7	
Month post Tx	0 - 3	3	6	8	9	10	12	18	
Randomization			X						

Treatments				
CNI group				
- Everolimus		center practice	C0-h level: 5 – 10 ng/mL	
- CNI (Cyclosporin A/ Tacrolimus)		acc. to blood level *	acc. to blood level *	acc. to blood level *
- MPA		center practice	none	None
- Steroids		0.05 – 0.3 mg/kg	0.05 – 0.3 mg/kg Prednisolone or equivalent	
CNI-free group				
- Everolimus		center practice	C0-h level: 5 – 10 ng/mL	
- CNI (Cyclosporin A/Tacrolimus)		acc. to blood level *	CyA: C0 level of ≤ 75 ng/mL for 8 weeks, then removal Tac: C0 level of ≤ 5 ng/mL for 8 weeks, then removal	None

- MPA		center practice	MMF 1.5 – 3 g/d OR EC-MPS 1440 – 2880 mg/d	MMF 1.5 – 3 g/d OR EC-MPS 1440 – 2880 mg/d
- Steroids		0.05 – 0.3 mg/kg	0.05 – 0.3 mg/kg Prednisolone or equivalent	

BL

= Baseline visit: day of randomization – Month 6 post Tx

CNI Group: treatment post randomization: Everolimus + Cyclosporin A/Tacrolimus + corticosteroids

Cyclosporin A Dosage: Month 1 - 6: C0-h levels 100 – 200 ng/mL
Month >6: C0-h levels 50 – 150 ng/mL
(cf. section 6.5.2)

Tacrolimus Dosage: Month 1 - 6: C0-h levels 5 - 10 ng/mL
Month >6: C0-h levels 3 - 8 ng/mL

CNI-free Group: treatment post randomization: Everolimus + MPA + corticosteroids

Cyclosporin A Dosage: Month 1 - 6: C0-h levels 100 – 200 ng/mL
Month 6 - 9: C0-h levels ≤75 ng/mL
(cf. section 6.5.2)

Tacrolimus Dosage: Month 1 - 6: C0-h levels 5-10 ng/mL
Month 6 - 9: C0-h levels ≤5 ng/mL

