6.5.7 Emergency unblinding of treatment assignment

Not applicable, since this is an open-label trial.

7 Visit schedule and assessments

Table 7-1 lists all of the assessments and indicates with an “X” the visits when they are performed. All these obtained data must be supported in the patient’s source documentation.

Table 7-1 Assessment schedule

Phase	Prephase	Study Drug Treatment					
		SCR	BL	Switch	Maintenance		
Period	1	2	3	4	5	6	7 ¹ /7.1 ²
Visit	1	2	3	4	5	6	7 ¹ /7.1 ²
Month post Tx	3	6	8	9	10	12	18
Informed consent	X						
Inclusion/ exclusion	X		X				
Randomization			X				
Demography	X						
General medical history	X						
Renal history (information on dialysis etc.)	X						
Transplantation information	X						
Physical examination	X	X		X			X
Vital signs	X	X	X	X	X	X	X
Endomyocardial biopsy		X		X		X	X
ECG	X	X		X		X	X
Study medication check		X	X	X	X	X	X
Laboratory test:							
- Hemat. / Biochemistry	X	X	X	X	X	X	X
- Viral Serology	X	X ³	X ³	X ³	X ³	X ³	X ³
- Pregnancy test ⁴ (β-HCG)	X	X	X	X	X		X
- Blood sampling for frozen storage (2-5 mL EDTA blood)	X	X		X			X
- Urinalysis (proteinuria)	X	X		X			X
Drug concentration (C0-h)							
Tacrolimus/ Cyclosporin A ⁵	X	X	X	X	X	X	X
Everolimus	X	X	X	X	X	X	X
Comments				as necessary			
Echocardiogram				as necessary			
Hospitalization ⁶				as necessary			
AEs				as necessary			
SAEs				as necessary			
Infections				as necessary			
Concomitant therapy				as necessary			
Positive inotropic effect or vasoactive treatment				as necessary			
Immunosuppressive therapy				as necessary			
Rejection episodes				as necessary			
Hemodynamic compromise				as necessary			
MACE				as necessary			
End of study ^{1/2}							X

SCR: Screening visit: Month 3 post Tx

BL: Baseline visit: day of randomization, Month 6 post Tx

- 1) At end of study (Month 18 post Tx) or at timepoint of discontinuation for patients with premature discontinuation of per protocol treatment
- 2) At Month 18 post Tx: Only for patients who prematurely discontinued the per protocol treatment
- 3) Only CMV-status (including pp65 Ag)
- 4) Only in women of childbearing potential
- 5) To be assessed only if Cyclosporin A or Tacrolimus is administered at that visit. C0-h levels have to be determined at all indicated timepoints.
- 6) Hospitalization: see [section 7.8](#), Resource utilization

Patients should be seen for all visits on the designated day or as close to it as possible. However, timely intervals of \pm 1 week will be regarded acceptable.

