9. Venous blood will be drawn for measurement of the C0-h levels of Cyclosporin A or Tacrolimus and Everolimus.
10. Venous blood will be drawn for frozen storage until end of trial (2 EDTA-tubes, **2-5 mL**).
11. In woman of childbearing potential a pregnancy test will be performed (β -HCG).
12. Urinalysis for proteinuria will be performed (spot urine sample for protein/creatinine ratio may be used).
13. Changes in Concomitant medications / significant non-drug therapies will be recorded.
14. (Changes in) immunosuppressive medication will be recorded.
15. Information on rejection episodes, hemodynamic compromise, MACE, hospitalization, infections, and other (S)AEs that occurred since the last visit will be recorded.

Switch of immunosuppressive regimen - Visit 3 (Month 8 post Tx)

This visit may be performed within a time window of \pm 1 week.

1. Vital signs will be measured.
2. Venous blood will be drawn for measurement of hematology and biochemistry.
3. In woman of childbearing potential a pregnancy test will be performed (β -HCG).
4. Venous blood will be drawn for measurement of viral serology (CMV status including pp65 Ag)
5. Venous blood will be drawn for measurement of
 - Everolimus C0-h level in all patients
 - Cyclosporin A C0-h level, only in patients of the CNI group

- Tacrolimus C0-h level, only in patients of the CNI group
- 6. Changes in concomitant medications / significant non-drug therapies will be recorded.
- 7. Changes in immunosuppressive medication (including study drug dosage) will be recorded.
- 8. Information on rejection episodes, hemodynamic compromise, MACE, hospitalization, infections, and other (S)AEs that occurred since the last visit will be recorded.

Maintenance Period - Visits 4, 5 and 6 (Month 9, 10, 12 post Tx)

These visits may be performed within a time window of \pm 1 week.

- 1. Vital signs will be measured.
- 2. An endomyocardial biopsy will be performed (only visits 4 and 6).
- 3. A 12-lead ECG will be written (not at month 10, Visit 5).
- 4. Venous blood will be drawn for measurement of hematology and biochemistry.
- 5. Venous blood will be drawn for the measurement of viral serology (only CMV-status including pp65 Ag).
- 6. Venous blood will be drawn for measurement of
 - Everolimus C0-h level in all patients
 - Cyclosporin A C0-h level, only in patients of the CNI group
 - Tacrolimus C0-h level, only in patients of the CNI group

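### As read from the PDF, Table 7-1 leaves the pregnancy test unmarked at Month 12, although the text for Visits 4 to 6 requires it there

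*Protocol*

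**What the plan says.** Three current parts of the protocol set the pregnancy-test schedule.

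- **Section 6.5.1, recommendations for female patients.** Testing in women of childbearing potential is to be "done at Screening, Baseline, Switch and following study visits (Assessment Schedule Table 7-1". The next sentence adds that the β-HCG test "is mandatory for all female patients in this trial at all indicated visits (Table 7-1". Both sentences point to the table.
- **Section 7, Table 7-1.** The section opens with "Table 7-1 lists all of the assessments" and uses an X to show the visits. The pregnancy-test row, as read, has an X at Months 3, 6, 8, 9, 10 and 18 and nothing at Month 12. Footnote 4 to the row, "Only in women of childbearing potential", limits who is tested, not when.
- **Section 7, visit list headed "Maintenance Period - Visits 4, 5 and 6 (Month 9, 10, 12 post Tx".** Item 7 calls for the β-HCG test in women of childbearing potential and names no visit as an exception. The same list does state exceptions elsewhere: "An endomyocardial biopsy will be performed (only visits 4 and 6" and "A 12-lead ECG will be written (not at month 10, Visit 5".

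The Amendment 4 rationale describes the test as applying at screening, baseline, switch and every study visit. I use it only as a sign of intent. The disagreement lies between Table 7-1 and item 7, both current text.

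**The concern.** The list for Visits 4 to 6 writes out its visit limits where it has any, so the absence of a limit on item 7 reads as a requirement at all three visits, Month 12 included. The table shows the opposite for Month 12. Because section 6.5.1 makes the test mandatory at the visits the table indicates, a site that schedules from the table could reasonably conclude that no test is due then.

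The stake is a safeguard against exposure in pregnancy. Section 6.5.1 describes MPA as a strong human teratogen. Table 6-1 keeps the CNI-free arm on MPA throughout maintenance, so Month 12 falls within exposure. The patients concerned are women of childbearing potential taking MPA: by protocol, those in the CNI-free arm. Section 7.1 leaves immunosuppression to the investigator once the per-protocol regimen is stopped, so a former CNI-arm patient given MPA off protocol would also be concerned.

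**Working it through.** The plan states no figure on this point, so the check is a cell-by-cell comparison followed by simple counts.

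**Pregnancy test, table against visit text**

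| Visit | Month | Table 7-1 as read | Section 7 visit text |
|---|---|---|---|
| 1 | 3 | X | required |
| 2 | 6 | X | required |
| 3 | 8 | X | required |
| 4 | 9 | X | required |
| 5 | 10 | X | required |
| 6 | 12 | blank | required |
| 7 | 18 | X | required |

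The table marks 6 of 7 visits and the text requires 7 of 7. They differ only at Month 12.

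**Scheduled tests after Baseline**

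- Table: Months 8, 9, 10, 18 = 4 tests.
- Text: Months 8, 9, 10, 12, 18 = 5 tests.

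**Longest interval between scheduled tests**

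- Table: 18 − 10 = 8 months.
- Text: 18 − 12 = 6 months.
- Difference: 8 − 6 = 2 months.

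**How far the table as read can be trusted.** I compared every row of Table 7-1 that has a counterpart in the visit text, 19 rows in all. The study medication check row has no counterpart and was left out, as were the rows scheduled only as necessary. Marks, table/text: consent 1/1, eligibility 2/2, randomization 1/1, demography 1/1, medical history 1/1, renal history 1/1, transplantation information 1/1, physical examination 4/4, vital signs 7/7, biopsy 4/4, ECG 5/5, hematology and biochemistry 7/7, viral serology 7/7, pregnancy 6/7, frozen storage 4/4, urinalysis 4/4, CNI level 7/7, everolimus level 7/7, end of study 1/1. The sums are 71 and 72.

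- Number of marks agrees in 18 of 19 rows; only the pregnancy row is short.
- Position of marks agrees in 16 of 19 rows. In two of the other three, the second eligibility mark and the randomization mark sit under Month 8 instead of Month 6. Those marks moved by one column; neither was lost.
- The CNI-level row differs from the text in who is tested, not in which visits are marked. Footnote 5 reads "To be assessed only if Cyclosporin A or Tacrolimus is administered at that visit", whereas the text from Visit 3 on names the CNI group only.

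A column shift does not explain the blank. The pregnancy row keeps all seven cells and ends with an X under Month 18, and the neighbouring laboratory rows match their visit text. A single lost mark remains possible.

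**How many women.** The documents do not say. The Amendment 4 rationale gives 160 patients randomized when it was prepared, and SAP section 1.1 gives 162 at the end of enrollment, so 162 − 160 = 2 came later. If the Month 12 test was introduced by that amendment (an assumption), it reaches those 2 and any of the 160 who had not yet passed Month 12.

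**The case against.** The strongest reply is that the point rests on one empty cell in a table read by a program, and that the same table visibly misplaces two other marks. Agreement in 18 other rows cannot show whether this one cell is blank in the PDF. The Amendment 4 rationale says the added tests went into both section 7 and Table 7-1, which fits a lost X about as well as an omission by the authors. This stands. It limits confidence and makes the PDF check the first step, but it does not remove the disagreement in the text as it can be read.

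The second reply is that the plan already covers Month 12. Item 7 requires the test, section 6.5.1 speaks of the visits after the switch, tests are repeated when clinically needed, and two contraceptive methods are required. Most of this stands too. Section 6.5.1 is the weaker support, since both its sentences refer back to the table. Item 7 is clear by itself, so an omission requires a site to follow the table and overlook its visit instructions.

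The 8-month figure counts scheduled tests only. Tests repeated after a reported gap in contraception, or done at an early-discontinuation visit, would shorten it.

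A reader might infer more than the documents support in three ways:

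- **That the protocol drops the Month 12 test.** It does not; item 7 requires it.
- **That only the CNI-free arm is concerned.** This is too absolute, given the investigator's discretion in section 7.1.
- **That trial results are at risk.** Nothing here touches GFR, its analysis or the sample size.

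**Conclusion.** The point holds as a low-priority internal inconsistency of an operational kind, with medium confidence. As read, Table 7-1 and item 7 for Visits 4 to 6 disagree on one test at one visit, and section 6.5.1 ties the mandatory test to the table that has the gap. Its size is one test per woman concerned and at most 2 further months between scheduled tests. The number of women is unknown and may be small. The conclusion assumes that the blank cell is in the PDF and that item 7, rather than the table, states what was intended. The unqualified item and the Amendment 4 rationale both favour that assumption.

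**What to change.** Look at the pregnancy-test row of Table 7-1 in the PDF. If the Month 12 cell carries an X there, nothing needs to change. If it is blank, add an X so that the table agrees with the visit text. The cost is one table cell. The visit text already requires the test and venous blood is already drawn at Month 12, so no visit or blood draw is added. The correction helps only patients who have not yet had their Month 12 visit. Amendment 3 already made typographical corrections to this table, so there is precedent for handling it this way.
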